Women age 18 or above are eligible if this is their first birth. Women with high risk pregnancies will be ineligible for participation, and enrolled women will be removed from the study if they deliver preterm, suffer severe maternal complications (c-section or hospitalization), or they or their baby are otherwise sick in the first week postnatal. When women give birth, the ASHA and facilitator will inform the research team, and women will be assigned to groups based on date of delivery to cluster delivery dates in within approximately two weeks.

Back-end data will be captured from all participants. A brief phone survey with all participants and in-depth interviews with half of participants will be conducted after 2 months (~ 8 group meetings).

Surveys and backend data: All 48 respondents will be called via phone to participate in a short (10 min) survey about their experiences with MeSSSSage group components, including preferences regarding functions and modalities and level of satisfaction with each, using likert-type response scales (1-5). Data will be recorded on a tablet. We will calculate means and standard deviations for each preference and function variables. Each group discussion will be audio recorded, transcribed, and translated into English. We will analyze group discussion content for function, using Atlas.ti. We will review intervention engagement including text-messaging (number

and topic), number of participants per session, engagement with the health worker and each other, etc. The study team has previously analyzed prior technological study data; we will use a similar method, in STATA v15.

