Table 2: *MeSSSSage* components to be tested in feasibility and acceptability assessment (Phase 2).

	Arm 1	Arm 2	Arm 3	Control
Real-time live voice call group meeting: Interactive educational program with scripted didactic component plus discussion/question. Lead and moderated by health professional.	X		X	
Text-based, asynchronous, on-demand social support: App-based small group text-based communication. Moderated by health professional.		X	X	
Standard of care: 3 visits in the first 7 days postnatal (facility and home)	X	X	X	X

Procedures: Unless found not feasible or acceptable within Phase 1 activities, women will be recruited using the approach described above (Aim 1). At the time of enrollment, the study protocol will be described to the women per informed consent procedures. Written confirmation will be obtained from interested women and their phone numbers will be collected (and tested). Women without a phone will be provided with a phone and all participants' airtime will be covered for the length of the 6-month research project. Women who consent will be randomly enrolled into 1 of the 4 study arms using a random number generator. We will test each study condition using 2 groups of women, with intervention initiation staggered 1 month apart. Women in the control group will receive the standard of care. All women will be given 50 Indian Rupees for participation in each session (in addition to airtime and phone if needed), and ASHAs will receive 150 Indian Rupees for moderating each session. Assessment of feasibility and acceptability (Aim 2) and preliminary effectiveness (Aim 3) will be accomplished using mixed-methods including quantitative surveys, in-depth interviews, and technology assessment.

Survey data collection: Baseline and endline surveys will be administered by a research assistant in the respondent's home. Endline survey will be collected roughly 6 months postnatal, after potential participation in ~24 *MeSSSSage* sessions (details to be determined during Phase 1). We will capture women's health record cards and ASHA registers to validate self-reported health outcome data. Data will be collected on a tablet using the secure REDCap mobile research administration app, stored in a password protected database at UCSF, and no identifiable information will be included with analytic datasets (identifiable data will be stored separately).

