Recruitment. Study participants will be recruited by a team consisting of an Accredited Social Health Activists (ASHA) and a research assistant, overseen by the SWACH project and principal investigators. ASHAs are familiar with the women in this study population, as they already provide information and support about health to them in the community. Primiparous women will be recruited in their last month of pregnancy during the ASHA's regular home visit. At the time of enrollment, the study protocol will be described to the women following informed consent procedures and written informed consent will be obtained from interested women. Consent will also be obtained from family members given the cultural practices in the study population. Names and contact information will be collected and stored in a password protected and encrypted computer in a locked facility.

For Aims 2 and 3 (Piloting the intervention), We will recruit for the three intervention and the one control arms using a staggered approach, recruiting one group for each arm in month one of the intervention period and one group for each arm in month two of the intervention period, to result in a total of eight groups (two per condition), for a total of 160 participants. Such a staggered approach is preferred to ensure that women are enrolled into groups with other women whose infants are similarly aged, and is feasible given the population size of our study districts.

Retention plan (i.e. Attrition reduction plan). We will carefully monitor attrition in this study.

Retention is facilitated by engagement of the ASHA, who has familiarity and experience working with the community, and previous knowledge of the participants. Contact information, including names, addresses, and phone numbers, will be collected at baseline to facilitate tracking. One of the aims of this study is to measure participation and engagement in the intervention, thus, we will be measuring retention as one of our outcomes.

PROTECTION OF HUMAN SUBJECTS

Risks to Human Subjects

Human Subjects Involvement and Characteristics of Potential Subjects

The proposed two phased project will enroll a total of (160+48) women to develop the optimal design and then understand the acceptability, feasibility, and preliminary effectiveness of the MeSSSSage intervention on maternal and infant health outcomes in India.

Inclusion criteria are:

Phase 1: 18+ years old, primiparous (pregnant with their first birth)

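### Phase 2 allocation: no restriction is described that would ensure 40 women per arm and even monthly groups, and neither the time of allocation nor the reach of the Aim 1 removal rule is settled

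*Protocol*

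**What the plan says.** **Target sizes.** Protocol, Specific Aims, Aim 2 plans 160 women, 40 in each of four arms. The Recruitment and Retention Plan describes staggered recruitment, "recruiting one group for each arm in month one of the intervention period and one group for each arm in month two", giving eight groups, two per condition.

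**Allocation.** Protocol, Phase 2, Procedures: "Women who consent will be randomly enrolled into 1 of the 4 study arms using a random number generator". The SAP does not describe allocation.

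**Timing.** Under Recruitment: "Primiparous women will be recruited in their last month of pregnancy". The section on inclusion of women and minorities adds that the intervention starts postpartum. No sentence dates allocation relative to birth. The Aim 1 procedures place group formation after delivery: "women will be assigned to groups based on date of delivery to cluster delivery dates in within approximately two weeks". The Recruitment section says the staggering ensures that "women are enrolled into groups with other women whose infants are similarly aged".

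**Removal.** The Aim 1 procedures state that "enrolled women will be removed from the study if they deliver preterm, suffer severe maternal complications (c-section or hospitalization", or if "they or their baby are otherwise sick in the first week postnatal". The Phase 2 procedures say that, unless Phase 1 shows otherwise, "women will be recruited using the approach described above (Aim 1"). The Phase 2 inclusion criteria, under Protection of Human Subjects, list only age and first birth; they neither repeat nor withdraw the removal rule.

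**Analysis.** Neither document names an analysis set. The regression model in both has terms for voice, text and their interaction, and none for wave.

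**The concern.** There are two separate issues.

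The first is balance. A random number generator applied woman by woman fixes the probability of each arm, not the arm size. This intervention is delivered in groups, and the Sample Size section says that size was chosen partly with interpersonal interaction in mind. Aim 2 then compares participation and engagement between the three intervention arms. If one arm happens to run groups of 14 and another groups of 26, group size is mixed up with the component being compared.

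The second is what happens between allocation and the start of the groups. If women are allocated at consent in late pregnancy, and the Aim 1 removal rule carries over, some are removed after randomisation. One criterion, being otherwise sick in the first week, is a judgement, and no blinding of the person who makes it is described. Without a stated analysis set, a reader could not tell which women each result describes. The pilot is meant to inform a larger trial, so its participation and retention figures need a clear basis.

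**Working it through.** **1. Reproduce the plan's figures.** 4 arms × 40 = 160 (Specific Aims, Aim 2). 4 arms × 2 groups = 8 groups (Recruitment), so 160/8 = 20 women per group and 80 per monthly wave. The 20 is derived, not stated. The overview of Phase 2 gives three groups per intervention modality while also giving eight in total, which conflicts with two per condition. There is no power calculation to reproduce; the plan disclaims one.

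**2. Unrestricted allocation.** Assumption: each woman has probability 1/4 for each arm, independently, with 80 women per wave.
- Arm size is Bin(160, 1/4): mean 40, SD = √(160 × 0.25 × 0.75) = 5.5, exact 95% range 30 to 51.
- Monthly group size is Bin(80, 1/4): mean 20, SD = √(80 × 0.25 × 0.75) = 3.9, exact 95% range 13 to 28.
- In 400,000 simulated allocations, the largest and smallest arms differ by 13 on average (95% range 4 to 25).
- At least one group in a given wave has 15 women or fewer in 45% of allocations. Over two waves this is 1 − (1 − 0.454)² = 70%.

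**3. Cost in precision.** The variance of a two-arm contrast, proportional to 1/n₁ + 1/n₂, averages 1.02 times its value at 40 v 40. The standard error is therefore about √1.02 = 1.01 times as large, a loss of about 1%.

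**4. Restricted allocation.** Permuted blocks of 4 and 8 in random order within waves of 80 (20,000 runs) gave 19 to 21 per group and 38 to 42 per arm every time. Blocks of 4 alone give exactly 20 and 40 when a wave holds exactly 80 women.

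**5. Removal after allocation.** Removal after randomisation needs both of two conditions.

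| | Removal rule applies in Phase 2 | Rule does not apply |
|---|---|---|
| Allocation before birth | Women removed after randomisation | No such removals |
| Allocation after the first week | Removals precede allocation | No such removals |

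The documents do not say which cell holds. They also give no removal rate, so the following only illustrates the first cell, at assumed rates of 10%, 20% and 30%:
- Of 40 allocated, 40 × (1 − q) leaves 36, 32 or 28 per arm.
- With an assumed 10% lost among the rest, retention is 0.9 × (1 − q) = 81%, 72% or 63% of randomised women, against 90% of those not removed.

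No bias estimate is given: it would need the frequency of first-week sickness, its relation to the outcomes and the difference in removal between arms, none of which the documents supply.

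**The case against.** A random number generator is a tool, not a method: it can produce a blocked or fixed-size list as easily as a sequence of independent draws. The stated 40 per arm and one group per arm per month show that equal allocation is intended. A reader might infer that the plan uses simple randomisation and will miss its arm sizes. The documents do not support that; they support only that nothing written ensures the sizes. This part of the objection stands, and the ranges in the working are conditional on unrestricted allocation.

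A reader might also infer that Phase 2 excludes women after randomisation and so biases its results. That needs both conditions above. Phase 2 expressly adopts how women are recruited, which need not include the removal rule, and its own criteria list only age and parity. Allocation before birth fits consent in late pregnancy, but forming groups by delivery date and infant age leaves later allocation open. This also stands: the exclusion issue is conditional. Even where both conditions hold, the intervention starts postpartum, so preterm birth and c-section are unlikely to depend on arm. The likely route to bias is the judgement about sickness.

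Finally, this is an unpowered pilot that plays down significance testing, and no stated threshold changes; the 70% criterion concerns enrolment. The missing retention denominator alone would be a missing detail. None of this answers the point about group size: even groups matter to a pilot of a group intervention, and blocking costs almost nothing.

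**Conclusion.** The concern holds as a gap in the design with an easy improvement. The plan sets equal arms and groups but describes nothing that ensures them. If allocation is unrestricted, expect 30 to 51 women per arm and 13 to 28 per monthly group (95% ranges), with about a 1% rise in standard error. The practical harm is uneven group size when Aim 2 compares participation and engagement between arms.

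The time of allocation and the reach of the removal rule are unresolved. Removal after randomisation is a possibility to be closed off, not an established feature of the plan; its bias is likely small and cannot be quantified from the documents. The retention figures above rest wholly on assumed rates. No power claim is affected.

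**What to change.** 1. Allocate by permuted blocks (for example of 4 and 8) within each monthly wave, and add wave to the regression model in the protocol and SAP.
2. Reconcile the Aim 1 procedures, the Phase 2 procedures and the Phase 2 inclusion criteria on whether the removal rule applies in Phase 2. Which rule is right is a clinical matter for the investigators. Reconcile the number of groups per condition at the same time.
3. State when allocation occurs. The preferred time is after the first-week check, with consent and the baseline survey taken in pregnancy; any removals then precede randomisation.
4. Define the analysis set as all randomised women, in the arm to which they were allocated.
5. If allocation stays in pregnancy, follow and analyse all randomised women where possible, report removals by arm with reasons, and give retention with and without removed women.

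**Cost.** A protocol amendment and a blocked allocation list. Later allocation adds a step that must fit between the first-week check and group start, and the component training planned at enrolment may have to move to it. Some consented women would never be allocated: if the rule applies and 10% to 30% are removed (assumed), allocating 160 needs 160/(1 − q) = 178 to 229 consented women, so 18 to 69 are not allocated.

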In-depth interviews: Additionally, in-depth interviews (IDIs) will be conducted with a selection of 10 women from each intervention condition (30 IDIs), purposively sampled based on high/low participation rates determined by the end line survey. We will collect data on experiences with *MeSSSSage* and how to improve it.

Technology assessment: Finally, we will collect and analyze the quantitative backend data from the prototype to gain more insight into women's participation in the intervention, including attendance and level of participation

in group interactive educational sessions, use of mobile social support platform (number of posts, frequency, topic), etc. Text data from transcripts of the educational sessions and content of group messaging will be analyzed for content in order to understand primary educational needs and interests for postnatal women.

Group moderator survey and interview: ASHA facilitators moderating the groups will be asked to respond to a short questionnaire after each group session to understand: preparation and delivery time, content, efficiency, acceptability and satisfaction with the group model, perspectives of impact, challenges, and any follow-up/referral necessary.⁴⁰ Regarding facilitation of groups that receive the text-based messaging intervention component only, ASHA facilitators will report on experiences in the prior week. We will conduct monthly semi-structured interviews with each of the ASHA facilitators to understand their preferences for group components, experiences preparing for and conducting the sessions, and their perspectives on mobile provision of education, care, and support.

Measures: The baseline survey content will include sociodemographic characteristics and knowledge about maternal and infant health, self-efficacy, and perceived social norms regarding MCH-related health promoting behaviors. The endline survey will include acceptability questions such as women's satisfaction with and perceptions of *MeSSSSage*, maternal and infant knowledge-, behavior-, and health-related questions including about breastfeeding, complementary food introduction, immunization, family planning uptake, maternal physical and mental health, etc. which have previously been used in this setting (Table 3)⁴.

Table 3: Participant survey measures (Phase 2)

Category	Measures

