Sociodemographic characteristics	Age, age at marriage, educational attainment, caste, language spoken, household assets, women's status/decision-making, social support and relationship quality.
Health-related knowledge (effectiveness)	Knowledge on maternal and neonatal danger signs, best practices for infant care, family planning.
Health-related behaviors (effectiveness)	Breastfeeding and complementary food introduction practices (breastfeeding initiation, length of exclusive breastfeeding, length of breastfeeding, timing of complementary food introduction), appropriate management of early childhood illnesses.
Health outcomes (effectiveness)	Early childhood immunization, postnatal depression and anxiety, postnatal family planning adoption.
Intervention perspectives (feasibility, acceptability)	Self-reported engagement in intervention components and topics, satisfaction with intervention components, likelihood of participating again, likelihood of recommending program, value on knowledge and social support gained from participation.

Analysis. *Aim 2. Feasibility and acceptability of the optimized MeSSSSage intervention components.* We will use a mixed methods approach, triangulating data from quantitative baseline and endline data, qualitative IDIs, and technology assessment. Feasibility and acceptability will be measured by participation rates at each session, participation trajectories over time, and user engagement (via technology assessment backend data). Women's reports of use and satisfaction (survey and IDI will shed light on barriers and facilitators to participation. Moderator acceptability will be assessed by satisfaction, fidelity to topic/content based on protocol and perspectives on impact. We will test for differences in feasibility and acceptability between the three intervention arms to understand if both components (group meetings and text) or only one is the best approach, using ANOVA for continuous outcomes and chi-square or Fisher's exact tests, as appropriate, for categorical outcomes.

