Aim 3. Preliminary effectiveness of the MeSSSSage intervention components on six-month MCH outcomes. Using the quantitative survey data, we will statistically evaluate differences by study arm in improvements in women's knowledge, behaviors, and maternal and child health outcomes, compared to the control group (including effect sizes, controlling for relevant socio-demographics as necessary). Figure 1 displays the outcomes that are theoretically related to our intervention targets. Our main *knowledge* outcome will be a composite score representing the proportion of correct answers from a knowledge scale on breastfeeding, newborn and infant care, maternal and infant danger signs, newborn care, and family planning, topics that will be covered within our interactive educational group component. Our main *behavior* outcome will be self-reported exclusive breastfeeding at 6 months. Our main *health related* outcomes will be: (1) completion of early childhood immunization schedule; and (2) postnatal family planning uptake. We will measure women's social support and related mental health status (depression and anxiety) using scales that have been previously validated in similar populations such as the Hopkins Symptom Checklist⁴¹ and the Multidimensional Scale of Perceived Social Support⁴². Finally, women's empowerment will be measured using decision-making and mobility scales.^{43,44}

Sample Size. This pilot development study is not formally powered to detect significant differences in outcomes, but will give insight into directionality of changes. The per group sample size was selected based on feasibility

of recruitment, intervention delivery, and the interpersonal interaction important for a group-focused intervention. The sample is sufficiently large to assess the feasibility and acceptability outcomes through descriptive statistics.

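### Immunization completion is compared between arms on the mother's survey answer; a card-first definition with a rule for discordant or missing records would limit differential over-reporting

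*Protocol*

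**What the plan says.** In the Protocol's Analysis section, Aim 3 names "completion of early childhood immunization schedule" as the first of two main health-related outcomes. The comparison is described there as follows: "Using the quantitative survey data, we will statistically evaluate differences by study arm".

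Immunization is a survey item. The Measures paragraph says the endline survey contains "health-related questions including about breastfeeding, complementary food introduction, immunization, family planning uptake", and Table 3, which lists participant survey measures, has the row "Early childhood immunization, postnatal depression and anxiety, postnatal family planning adoption" under health outcomes.

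On collection, the Survey data collection paragraph of Phase 2 states: "Baseline and endline surveys will be administered by a research assistant in the respondent's home". The same paragraph gives the records their role: the team will capture "health record cards and ASHA registers to validate self-reported health outcome data".

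The SAP lists early childhood immunization under Preliminary effectiveness, without a data source or derivation. Neither document gives a rule for discordant records, a rule for women with no card, or any statement about masking of assessors.

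**The concern.** A woman knows whether she has been in a moderated call group or chat group. The Protocol's Significance section includes better childhood vaccination uptake among the hoped-for effects of group support. Women in the intervention arms may therefore be more inclined than controls to say that the schedule is complete.

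The setting adds to this. The question is put face to face by a research assistant, and the same endline survey asks about satisfaction with the programme, which reveals the arm. Research assistants also train women in the intervention components at enrollment (Low literacy among target population).

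Over-reporting that is equal in all arms does not create a difference where none exists. Over-reporting that differs by arm shifts the estimate towards the intervention, and a wide confidence interval does not reveal the shift. This matters because the pilot is meant to show the direction of change and to inform a larger trial. The team already plans to capture a record that may be less exposed to this problem, but the plan does not say that the record will determine the analysed value.

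**Working it through.** **Figures to reproduce.** None. The documents give no over-reporting rate, effect size, alpha or power for this outcome.

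**Inputs.**
- True completion p = 0.622 in every arm. This is the Haryana survey figure in the Significance section, used for illustration; it is not stated as a control-arm assumption.
- 40 women per arm, 160 in total (Aim 2).
- f = the extra share of true non-completers in an intervention arm who report completion. Assumed at 10%, 20% and 30%.
- Two-sided 0.05, no dropout and no clustering. All assumed.

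**False difference.** With no true effect, the reported rate in the intervention arm is q = p + f(1 − p), so the false difference is d = f(1 − p) = 0.378f.
- f = 10%: 0.10 × 0.378 = 0.0378, or 3.8 points
- f = 20%: 0.20 × 0.378 = 0.0756, or 7.6 points
- f = 30%: 0.30 × 0.378 = 0.1134, or 11.3 points

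**Chance of a nominally significant result.** For n per side, let m = (p + q)/2, s0 = √[2m(1 − m)/n] and s1 = √{[p(1 − p) + q(1 − q)]/n}. The chance is Φ[(d − 1.96·s0)/s1] + Φ[(−d − 1.96·s0)/s1].

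| f | Reported rate q | False difference | 40 vs 40 | 80 vs 80 |
|---|---|---|---|---|
| 0 | 62.2% | 0 | 5.0% | 5.0% |
| 10% | 66.0% | 3.8 points | 6.4% | 7.9% |
| 20% | 69.8% | 7.6 points | 10.9% | 17.2% |
| 30% | 73.5% | 11.3 points | 19.0% | 33.5% |

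The 80 vs 80 column is a pooled comparison of one factor. It applies when the excess follows that factor, for example in both voice arms but not in the text-only arm.

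**In the SAP's model.** With 0/1 indicators, an equal excess in all three intervention arms gives β1 = d and β2 = d. The combined arm also differs from control by d, so β1 + β2 + β3 = d and β3 = −d. The same bias would thus also appear as a false negative interaction.

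**Over-reporting among controls.** If a share g of control non-completers also over-report, the difference is (g + f)(1 − p) − g(1 − p) = f(1 − p), which is unchanged. For g of 10% to 20%, the chance at 40 vs 40 is 6.5% to 6.6% for f = 10% and 11.3% to 11.9% for f = 20%.

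**Scale.** The 95% half-width for an arm difference is 1.96 × √(2 × 0.622 × 0.378/40) = 21.3 points at 40 vs 40. Replacing 40 by 80 gives 15.0 points. Every false difference above is smaller than either.

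**After a card-first definition.** If every card is seen and cards are equally complete in all arms, differential self-report contributes nothing. If a share a of women have a usable card, equally in all arms and unrelated to completion or reporting, the remaining bias is (1 − a)·f·(1 − p). The documents do not give a.

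**The case against.** The other side has real points.

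- **Validation may include correction.** A reader might infer that the records have no effect on the analysed value. The Protocol does not say so; it is silent on what follows from a disagreement. What stands is that no rule is written, and a rule chosen after seeing the data by arm would add a further problem.
- **The outcome is not labelled self-reported.** Aim 3 attaches that label to exclusive breastfeeding and not to immunization. The questionnaire is not in the documents, so the interviewer might copy from a card. Still, Table 3, the Measures paragraph and the Aim 3 analysis all place immunization in the survey data.
- **The card may not be the right record.** A reader might infer that an objective, dated infant record is already in hand. The Protocol speaks of women's health record cards and does not say that they hold infant doses or dated entries, or how many women will have one. The definition must therefore depend on what the card shows.
- **Exposure to immunization messages is uncertain.** Vaccination is a target, but the topics listed in Aim 3 for the educational component do not name it, and the text-only arm has no scripted teaching. Heavy coaching in every intervention arm is not documented.
- **The ASHA register.** The Protocol says "ASHAs will receive 150 Indian Rupees for moderating each session", so the cadre is paid to moderate the groups. No passage says that the ASHA who keeps a woman's register also moderates her group, or that the two records are to be given equal weight. This supports caution about the register, not a finding that it is biased.
- **This is an unpowered pilot.** Significance testing is played down, and the illustrated bias is smaller than the sampling error. That limits the severity of the point. It does not remove it, because the pilot's purpose is to show direction.

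**Conclusion.** The point holds as a worthwhile, inexpensive improvement. As written, the mother's survey answer is the analysed value for a main health outcome, the captured records have only a validating role, and discordant or missing records have no rule. Differential over-reporting could bias both the direction and the size of the arm difference.

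The illustrated size is 3.8 to 11.3 points. It rests on assumed excess over-reporting of 10% to 30% among non-completers and on a state survey rate of 62.2%. It lies inside a half-width of about 21 points at 40 per arm.

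Two stronger readings are tempting. One is that the pilot will produce a false arm difference; the documents give no over-reporting rate in any arm, so only the possibility is shown. The other is that using the card would remove the bias; that requires card availability and completeness to be similar across arms, which the documents do not address.

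**What to change.** In the Protocol (Survey data collection, and Analysis, Aim 3) and in the SAP (Preliminary effectiveness), state that:

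1. Immunization completion is derived from the health record card wherever a card showing infant doses is seen at endline. The coding is done without access to the arm variable.
2. Where no such card is seen, the mother's report is used and the value is flagged.
3. The ASHA register is supporting evidence in a sensitivity analysis and does not rank above self-report in the main definition, because ASHAs are also paid to moderate the groups.
4. The analysis on self-report alone is kept as a second sensitivity analysis.
5. Card availability and card-versus-report agreement are tabulated by arm.

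The cost is a few sentences, the coding of records the team already plans to capture, and, if the endline form lacks it, a field for whether a card with infant doses was seen. No extra visit or participant is needed. There are drawbacks: doses given but not recorded are missed, some women will have no card, and bias can remain if card availability or completeness differs by arm. The table in item 5 shows differences in availability and agreement; it cannot fully reveal differences in how completely cards were filled in.

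### Phase 2 interviewees are selected on self-reported participation from the endline survey, which leaves out women without an endline survey although back-end participation data are already collected

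*Protocol*

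**What the plan says.** The rule is in the Protocol, Approach, Phase 2, In-depth interviews paragraph. It plans "a selection of 10 women from each intervention condition (30 IDIs" in total), with the women "purposively sampled based on high/low participation rates determined by the end line survey".

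Three other places in the Protocol bear on it:

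- **Timing and setting of the survey** (Survey data collection): "Endline survey will be collected roughly 6 months postnatal, after potential participation in ~24" sessions, and "Baseline and endline surveys will be administered by a research assistant in the respondent's home".
- **What the survey records about participation** (Table 3, intervention perspectives row): "Self-reported engagement in intervention components and topics".
- **What the platform records** (Technology assessment): "we will collect and analyze the quantitative backend data from the prototype", to learn about "women's participation in the intervention, including attendance and level of participation". The Aim 2 analysis paragraph then relies on this kind of measure: "Feasibility and acceptability will be measured by participation rates at each session, participation trajectories over time, and user engagement", and it names the back-end data as the source for engagement.

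The SAP says nothing about how interviewees are chosen, so the Protocol paragraph is the only rule.

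**The concern.** Aim 2 asks whether the intervention is feasible and acceptable. The Aim 2 analysis paragraph gives two sources for the women's own account of what helped or hindered participation: the survey and the interviews. The acceptability questions sit in the endline survey, so a woman who misses endline is absent from the first source. The interviews could have reached her, but because they are selected from the same survey they share its blind spot.

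The plan itself treats this kind of loss as relevant. The Retention plan makes retention an outcome, the Data-related risks paragraph lists systematic attrition as a risk, and the Feasibility paragraph (Protocol and SAP) says the results will shape retention procedures for the full trial. That last use needs accounts from women who left.

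A second weakness does not depend on attrition. High and low participation are judged by recall over about six months, told to a research assistant, while attendance and platform use are recorded anyway. Aim 2 intends to triangulate interviews with platform data. If the interview strata rest on a different measure, a woman interviewed as a high participant may be a low one in the logs, which weakens that comparison.

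**Working it through.** **The plan's own figure.** Interviews = 10 per arm × 3 intervention arms = 30, which agrees with the Protocol. With 160 women in 4 arms there are 160 / 4 = 40 per arm and 3 × 40 = 120 in the intervention arms, so the interviews cover 30 / 120 = 25% of them.

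**Who is in the frame under the written rule.**

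| Woman's situation | Endline survey | Back-end record | Selectable as written |
|---|---|---|---|
| Attends, completes endline | yes | yes | yes |
| Stops attending, completes endline at home | yes | yes (low use) | yes, as a low participant |
| Lost or withdrawn before endline | no | yes, up to the point she left | no |

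Only the third row is excluded.

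**How many that could be.** Neither document states an endline non-completion rate; the Recruitment and retention paragraph says only that no difficulty is expected. Let d be an assumed rate. Women outside the frame per arm = 40 × d, and over three arms = 120 × d.

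| Assumed d | Outside frame per arm | Outside frame, three arms | Left in frame per arm |
|---|---|---|---|
| 0% | 0 | 0 | 40 |
| 5% | 2 | 6 | 38 |
| 10% | 4 | 12 | 36 |
| 20% | 8 | 24 | 32 |

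**How far this could reach into the low participants.** Take the lowest quarter of an arm as 10 women. If every non-completer came from that quarter, the rule would remove 2, 4 or 8 of the 10 at 5%, 10% or 20%. If non-completion were confined to better attenders, it would remove none. The documents do not place the truth within these bounds.

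**Whether the interviews can still be filled.** Yes. Even at 20% there are 32 women per arm for 10 interviews. The issue is which women can be heard, not how many interviews can be done.

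**With back-end selection.** All 40 women per arm could be classed at any value of d, if all 40 were assigned to a group. Reaching a woman who has left would still need contact and consent.

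**The case against.** A reader might infer that women who dropped out can never be interviewed and that they are the lowest participants. The documents do not support either part. Endline is a home visit and does not run through the platform, so a woman who attended no session can complete it, be classed as low and be interviewed; low participants are a stated target of the sampling. Nothing ties a missing endline to low use, since a woman lost late may have attended many sessions. Nor does the text forbid other interviews; it simply describes none.

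A reader might also conclude that acceptability will look better than it is. That does not follow. Session-level participation and its course over time need no endline survey, so disengagement will show in the logs. Facilitators report challenges after each session and are interviewed monthly. The Recruitment and retention paragraph also has the ASHA contact women who seem to have stopped taking part and find out why. These sources cover part of the gap. The ASHA contact, however, is not described as a recorded and coded research interview, and ASHAs help to recruit the women, so it does not replace one.

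Back-end counts have a weakness of their own. In the text-only arm, a woman who reads but does not post could appear inactive, whereas self-report might capture her. That objection stands and is met in the fix. A further caution concerns women removed in the first week for preterm delivery or complications: if the Phase 1 removal rule carries over, their empty logs would say nothing about acceptability.

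**Conclusion.** The concern holds in a limited form. The written rule confines the interview frame to women with an endline survey and classes them on self-report, although a recorded measure of participation is already collected and serves the Aim 2 analysis.

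The number excluded is 0 to 8 of 40 per arm over an assumed non-completion range of 0% to 20%. That range is an assumption, and whether those women are low participants is unknown. The second weakness, classing by recall when recorded use is available, remains at 0%.

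No estimate, sample size or error rate is affected. The point concerns the qualitative part of Aim 2 in a pilot that is not powered for effectiveness. Severity is low to moderate, and the change is a cheap improvement.

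**What to change.** Reword the selection rule in the Phase 2 In-depth interviews paragraph so that:

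1. High and low participation are defined from the back-end data (session attendance and platform use), with self-reported engagement as a supplement where logs may miss passive reading in the text arm.
2. The frame is all women who were assigned to a group in the arm, whether or not they completed endline. Defining it by group assignment is meant to keep out women removed before the intervention began.
3. Some of the women approached are ones who stopped participating or missed endline, subject to contact and continuing consent. The number can stay flexible; the documents give no basis for a fixed quota.

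The total remains 30 interviews and no new data are needed. The cost is a short wording change and somewhat more field effort to reach women who missed endline, some of whom will not be found or will decline.
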